#### Table 6–2 Summary table of comparison between serology and IHA results

						Conventi	ional ELISA Tes	ts
				Sero-	Sero-pos	itive	Missing	Total
				negative	Sero-reduction	Others		
	60-Day	Negative		xx (xx.x%)	xx (xx.x%)	xx (xx.x%)	xx (xx.x%)	xx (xx.x%)
	(N=x)		Decreasing in	xx (xx.x%)	xx (xx.x%)	xx (xx.x%)	xx (xx.x%)	xx (xx.x%)
		Positive	titers					
		TOSITIVE	Non-decreasing	xx (xx.x%)	xx (xx.x%)	xx (xx.x%)	xx (xx.x%)	xx (xx.x%)
			in titers					
		Missing		xx (xx.x%)	xx (xx.x%)	xx (xx.x%)	xx (xx.x%)	xx (xx.x%)
		Total		xx (xx.x%)	xx (xx.x%)	xx (xx.x%)	xx (xx.x%)	xx (xx.x%)
ША								
Tasting	30-Day	Negative		xx (xx.x%)	xx (xx.x%)	xx (xx.x%)	xx (xx.x%)	xx (xx.x%)
resting	(N=x)		Decreasing in	xx (xx.x%)	xx (xx.x%)	xx (xx.x%)	xx (xx.x%)	xx (xx.x%)
		Positivo	titers					
		rositive	Non-decreasing	xx (xx.x%)	xx (xx.x%)	xx (xx.x%)	xx (xx.x%)	xx (xx.x%)
			in titers					
		Missing		xx (xx.x%)	xx (xx.x%)	xx (xx.x%)	xx (xx.x%)	xx (xx.x%)
		Total		xx (xx.x%)	xx (xx.x%)	xx (xx.x%)	xx (xx.x%)	xx (xx.x%)

In addition, McNemar's test will be performed by treatment regimen for all patients in FAS (Table 6–3) with the following categories:

- ELISA tests: cure (sero-conversion and sero-reduction) versus no cure;
- IHA test: negative or positive but decreasing in titers versus positive but non-decreasing in titers.

Table 6–3 McNemar's test on comparison between serology and IHA results for all patients in FAS

				Cor	nventional ELISA	Tests		
			Cure (sero- negative or sero- reduction)	No cure	Missing	Total	$\chi^2$	P-Value
	60-Day (N=x)	Negative or positive but decreasing in titers	xx (xx.x%)	xx (xx.x%)	xx (xx.x%)	xx (xx.x%)		
		Positive but non- decreasing in titers	xx (xx.x%)	xx (xx.x%)	xx (xx.x%)	xx (xx.x%)		
		Missing	xx (xx.x%)	xx (xx.x%)	xx (xx.x%)	xx (xx.x%)		
		Total	xx (xx.x%)	xx (xx.x%)	xx (xx.x%)	xx (xx.x%)	X.XX	X.XX
IHA Testing	30-Day (N=x)	Negative or positive but decreasing in titers	xx (xx.x%)	xx (xx.x%)	xx (xx.x%)	xx (xx.x%)		
		Positive but non- decreasing in titers	xx (xx.x%)	xx (xx.x%)	xx (xx.x%)	xx (xx.x%)		
		Missing Total	xx (xx.x%) xx (xx.x%)	xx (xx.x%) xx (xx.x%)	xx (xx.x%) xx (xx.x%)	xx (xx.x%) xx (xx.x%)	x.xx	X.XX

The same test would also be performed by treatment regimen in sero-positive subjects (Table 6–4). The categories for this test are

- ELISA tests: sero-reduction versus others (sero-positive that are not sero-reduction);
- IHA test: negative or positive but decreasing in titers versus positive but non-decreasing in titers.

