4.1 Objectives for part 1 (CHICO)

The primary objective of this Phase 3 clinical study is:

• To assess the superiority of a 60-day regimen of nifurtimox to historical untreated control at the 12-month follow-up (360 days from end of treatment [EOT]) as sero-reduction (defined as a ≥ 20% reduction in optical density [OD] measured by conventional enzyme-linked immune sorbent assay [ELISA]) compared to baseline in subjects ≥8 months to <18 years of age at randomization; or sero-conversion (defined as negative Immunoglobulin G [IgG] concentration) in all subjects³⁴

Secondary objectives of the study are:

³⁴ Text modified as per amendment 2

	Integrated Clinical Study Protocol	
	BAY A2502 / 16027	
03 NOV 2020	Version 11.0	Page: 25 of 259

- To assess the comparability of a 30-day regimen of nifurtimox to a 60-day regimen of nifurtimox as sero-reduction or sero-conversion at the 12-month follow-up (360 days from EOT)³⁵
- To evaluate the safety/tolerability profile of nifurtimox by laboratory parameters (hematology, blood chemistry, urinalysis), electrocardiogram (ECG) monitoring, vital sign measurements (blood pressure, heart rate, respiratory rate, temperature), adverse event (AE) monitoring, and physical examinations, including neurological examinations³⁶
- To evaluate the pharmacokinetics (PK)/pharmacodynamics (PD) of nifurtimox in children receiving the drug for treatment of Chagas' disease (to be described in a separate report)

Exploratory objectives of the study are:³⁷

- To assess the comparability of a 60-day regimen of nifurtimox to historical active control (benznidazole)³⁸ as sero-reduction or sero-conversion at the 12-month follow-up (360 days from EOT)³⁹
- To assess the comparability of a 30-day regimen of nifurtimox to a 60-day regimen of nifurtimox using quantitative polymerase chain reaction (qPCR) at the 12-month follow-up (360 days from EOT)⁴⁰
- To evaluate the relationship of conventional serology (as sero-reduction or sero-conversion) to qPCR using frequencies of matches and mismatches to assess agreement⁴¹
- To evaluate the relationship of non-conventional serology to conventional serology⁴²
- To evaluate the relationship of conventional serology to IHA^{43,44}

4.2 **Objectives for part 2 (CHICO SECURE)**

The primary objective of the LTFU part of the study is:

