10.3.2 Statistical and analytical plans

10.3.2.1 Part 1 (CHICO)

Efficacy

Primary efficacy analysis

The difference in the proportion of nifurtimox subjects with sero-reduction¹⁸³ or sero-conversion (60-day regimen) and the proportion estimated from historical data will be tested using a 2-sided 95% CI for a single proportion.

The null hypothesis H_0 is $p_{nifurtimox} = p_{placebo}$

The alternative hypothesis H_1 is $p_{nifurtimox} \neq p_{placebo}$, where p_t is the sero-conversion rate for treatment t.

¹⁸³ Text modified for clarity (Amendment 1)

	Integrated Clinical Study Protocol
	BAY A2502/ 16027
03 NOV 2020	Version 11.0

Page: 80 of 259

Superiority will be confirmed if the lower limit of the CI for the proportion of nifurtimox subjects (60-day regimen) with sero-reduction or sero-conversion is greater than the proportion of historical placebo subjects with sero-conversion.¹⁸⁴

Sero-conversion for the historical placebo control is estimated as 16% from cure rates as presented in two publications [15][16], using a number greater than the larger of the upper limits of the 95% CIs from the two studies. Further details about the derivation of these rates are provided in Section 10.4.¹⁸⁵

Secondary and exploratory efficacy analyses ¹⁸⁶

A secondary analysis will be done to compare the proportion of subjects with sero-reduction or sero-conversion for the 60-day and 30-day nifurtimox regimens. This will be performed using a 2-sided 95% CI for the difference of two independent proportions.

The analyses specified above will also be done using data from the EOT visit, and 3 and 6 months after EOT.

The relationship of conventional serology results to qPCR results will be done using frequencies of matches and mismatches on the determination of disease status, and phi-correlation and kappa coefficient to assess the degree of agreement. The relationship of non-conventional serology to conventional serology will be analyzed in the same way.¹⁸⁷ The results from IHA and conventional serology will also be compared. The details of secondary and exploratory efficacy analyses will be further specified in the SAP.^{188,189}

Demographics and baseline characteristics

Demographics and baseline characteristics will be summarized by treatment and total population, using descriptive statistics and frequency tables as appropriate.

Safety

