#### **Statistical Analysis Plan**

#### BAY No. A2502/IMPACT No. 16027 Page: 5 of 30

reduction (defined as  $a \ge 20\%$  reduction in optical density [OD] measured by conventional enzyme-linked immunosorbent assay [ELISA]) compared to baseline in subjects  $\ge 8$  months to < 18 years of age at randomization or sero-conversion (defined as negative Immunoglobulin G [IgG] concentration) in all subjects

Secondary objectives of the study are:

- To assess the comparability of a 30-day regimen of nifurtimox to a 60-day regimen of nifurtimox as sero-reduction or sero-conversion at the 12-month follow-up (360 days from EOT)
- To evaluate the safety/tolerability profile of nifurtimox by laboratory parameters (hematology, blood chemistry, urinalysis), electrocardiogram (ECG) monitoring, vital sign measurements (blood pressure, heart rate, respiratory rate, temperature), adverse event (AE) monitoring, and physical examinations, including neurological examinations
- To evaluate the pharmacokinetics (PK)/pharmacodynamics (PD) of nifurtimox in children receiving the drug for treatment of Chagas' disease

Exploratory objectives of the study are:

- To assess the comparability of a 60-day regimen of nifurtimox to historical active control (benznidazole) as sero-reduction or sero-conversion at the 12-month follow-up (360 days from EOT)
- To assess the comparability of a 30-day regimen of nifurtimox to a 60-day regimen of nifurtimox using qualitative polymerase chain reaction (qPCR) at the 12-month follow-up (360 days from EOT)
- To evaluate the relationship of conventional serology (as sero-reduction or seroconversion) to qPCR using frequencies of matches and mismatches to assess agreement
- To evaluate the relationship of non-conventional serology to conventional serology
- To evaluate the relationship of conventional serology to indirect haemagglutination assay (IHA)

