## 6.2.1.2 Secondary efficacy variables and analysis

Secondary efficacy variables include clinical signs/symptoms of Chagas' disease (see Appendix 9.1), concentration test for *T. cruzi* (for subjects < 8 months of age ), non-conventional serologic testing, and disease state determined by qPCR ("cure" defined as Not Detectable / "no cure" defined as Detectable).

All secondary efficacy variables, except signs/symptoms of Chagas' disease, will be summarized overall and by treatment regimen at each assessment time for each age stratum.

Signs/Symptoms of Chagas' disease will be summarized for each item (see Appendix 9.1).

The relationship of conventional serology results to qPCR results will be done using frequencies of matches and mismatches on the determination of disease status, and phicorrelation and kappa coefficient to assess the degree of agreement. The relationship of nonconventional serology to conventional serology will be analyzed in the same way. The following SAS code will be used:

PROC FREQ;

TABLES group\*cured / CHISQ AGREE;

WEIGHT counts;

RUN;

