## 6.2.1.3 Exploratory efficacy analysis and analysis

For the exploratory objective to assess the comparability of nifurtimox with benznidazole, the cure rate of 58% with a 95% CI (45%, 70%) from publication of de Andrade et al. in 1996 [2] will be referenced. If the lower limit of the same 95% CI for the primary efficacy variable (the 60-day nifurtimox regimen cure rate) is greater than 45%, nifurtimox will be deemed as comparable to benznidazole.

The comparison of conventional serology to IHA results will be done using a 3-by-3 table (Table 6-2) with the following categories:

- ELISA tests: sero-conversion and sero-positive (sub-categories: sero-reduction and others), where "others" refers to any sero-positive results that do not satisfy the definition of "sero-reduction".
- IHA test: negative and positive (sub-categories: titers decreasing and titers non-decreasing).

BAY No. A2502/IMPACT No. 16027

21 of 30

Page:

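### Beyond cross-tabulations, McNemar's test is the only statistic planned for conventional ELISA versus IHA, and it does not measure agreement

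*SAP*

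**What the plan says.** The objective in Protocol 4.1 is "To evaluate the relationship of conventional serology to IHA", and SAP 2.1 repeats it. Protocol 10.3.2.1 names no method. It says "The results from IHA and conventional serology will also be compared" and leaves the details to the SAP.

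SAP 6.2.1.3 sets out three displays, each by regimen:

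- **Table 6-2:** a descriptive table of ELISA category (sero-conversion, sero-reduction, other sero-positive) against IHA category (negative, positive with decreasing titers, positive with non-decreasing titers), with missing results shown.
- **Table 6-3:** as an addition to that table, "McNemar's test will be performed by treatment regimen for all patients in FAS". ELISA is reduced to cure or no cure. IHA is reduced to negative or decreasing against positive and non-decreasing.
- **Table 6-4:** "The same test would also be performed by treatment regimen in sero-positive subjects", with ELISA split into sero-reduction and others.

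Tables 6-3 and 6-4 print the cell counts with percentages, a chi-square and a p-value. No kappa, phi, percent agreement or confidence interval is specified for this pair of tests.

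SAP 6.2.1.2 treats two similar comparisons differently. For conventional serology against qPCR, and for non-conventional against conventional serology, it plans frequencies of matches and mismatches plus phi and "kappa coefficient to assess the degree of agreement", with the AGREE option in the SAS code.

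**The concern.** A relationship between two assays read on the same children is mainly a question of whether they sort each child the same way. McNemar's statistic uses only the two discordant cells, and only the difference between them. It is silent on how many children are discordant relative to the total, so it cannot describe that relationship.

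The comparison has some weight although it is exploratory. The overviews of Protocol Amendments 5 and 6 give the reason for the extra assay as an FDA request for a test to validate the ELISA results. ELISA carries the Part 1 primary endpoint (SAP 6.2.1.1), and the Part 2 primary endpoint needs recombinant ELISA and IHA both negative in the same subject (SAP 6.2.2.1). A reader who wants to know how far the two assays agree will turn to these tables and find a p-value as the only summary figure. That figure answers a different question.

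**Working it through.** The documents give no expected ELISA/IHA cross-classification, sample size or power for this comparison, so there is no planned figure to reproduce. The check is whether the p-value tracks agreement.

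**Inputs.** The first-arm size of 200 and the cure rate of about 55% come from Protocol 10.4 and serve only to give the examples a realistic scale. The two-sided alpha of 0.05 is from SAP 4.1. The cell counts are assumptions.

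**Layout** (IHA in rows and ELISA in columns, as in Table 6-3): *a* = both favourable; *b* = IHA favourable, ELISA no cure; *c* = ELISA cure, IHA unfavourable; *d* = both unfavourable; n = a + b + c + d.

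**Formulas.**
- McNemar chi-square = (b - c)² / (b + c), 1 degree of freedom.
- Observed agreement po = (a + d) / n.
- Chance agreement pe = r·s + (1 - r)(1 - s), with r = (a + b)/n and s = (a + c)/n.
- Kappa = (po - pe) / (1 - pe).

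**Agreement no better than chance, 60/50/50/40.**
- Chi-square = (50 - 50)²/100 = 0, p = 1.00.
- po = 100/200 = 0.500.
- r = s = 110/200 = 0.55, so pe = 0.3025 + 0.2025 = 0.505.
- Kappa = (0.500 - 0.505)/0.495 = -0.01.

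**Strong agreement, 100/2/14/84.**
- Chi-square = (2 - 14)²/16 = 144/16 = 9, p = 0.003 (exact 0.004).
- po = 184/200 = 0.92.
- r = 102/200 = 0.51 and s = 114/200 = 0.57, so pe = 0.2907 + 0.2107 = 0.5014.
- Kappa = 0.4186/0.4986 = 0.84.

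**Further tables by the same formulas.**

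| a/b/c/d | n | McNemar p | Agreement | Kappa |
|---|---|---|---|---|
| 100/10/10/80 | 200 | 1 | 90% | 0.80 |
| 10/90/90/10 | 200 | 1 | 10% | -0.80 |
| 110/8/0/82 | 200 | 0.005 (exact 0.008) | 96% | 0.92 |
| 30/25/25/20 | 100 | 1 | 50% | -0.01 |

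The tables 60/50/50/40 and 100/10/10/80 have the same margins (55% on both assays) and the same p-value of 1, yet kappa is -0.01 in one and 0.80 in the other. The last row shows that the behaviour is the same at 100 children, the planned size of the 30-day arm in Protocol 10.4.

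**The case against.** Four points can be made for the plan.

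- **The joint counts are shown.** A reader might infer that McNemar's test is the whole comparison. It is not: Table 6-2 comes first, McNemar's test is introduced as an addition, and Tables 6-2 to 6-4 print every joint cell. In the chance-agreement example the reader would see 100 of 200 children discordant next to p = 1, and could work out kappa. This stands. What is missing is a summary coefficient, not the information.
- **No rule is attached to the p-value.** A reader might infer that a non-significant result will count as validation of ELISA and a significant one as failure. No section says so. The word validate appears in the amendment overviews, and the current objective speaks only of a relationship. This also stands. Misreading is a risk, not a planned inference.
- **McNemar's test answers a relevant question.** The Part 1 endpoint is a single cure proportion, so it is useful to know whether the ELISA definition gives a systematically higher proportion than IHA. This stands, and it is a reason to keep the test.
- **The IHA objective does not use the word agreement, whereas the qPCR objective does.** This explains the difference only in part. The objective for non-conventional serology is also worded as a relationship, and it gets phi and kappa.

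**Conclusion.** The point holds in a limited form. For conventional ELISA against IHA, the SAP specifies no agreement coefficient, and the one statistic that it does specify cannot distinguish chance-level from strong agreement. The SAP gives no reason for treating this pair differently from the two pairs in 6.2.1.2.

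The worked tables show what is possible and do not forecast the trial's result, because the cell counts are assumed. The practical effect is small: this is one exploratory objective of Part 1, no decision rule depends on it, the counts needed to compute kappa will be printed anyway, and neither primary analysis changes. The documents do not support calling McNemar's test an error. It is an incomplete answer to the stated objective.

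**What to change.** In SAP 6.2.1.3, for Tables 6-3 and 6-4 and by regimen:

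1. Add overall percent agreement and kappa, matching what 6.2.1.2 does for qPCR and non-conventional serology.
2. Preferably add a 95% CI for kappa and the positive and negative percent agreement, naming the comparator. These go beyond what 6.2.1.2 names, so they would be new there too.
3. Compute these on children with both results, keeping the missing row and column as displayed now.
4. Keep McNemar's test, with a line saying that it checks for a systematic difference between the two proportions and is not a measure of agreement.

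The cost is a few lines of SAP text and two or three extra table columns. No new data are needed, and the AGREE option is already in the SAP's code.

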There are several choices for diagnosis of Chagas' disease and monitoring of drug efficacy after anti-parasitic treatment. Traditional parasitological methods, such as direct microscopic observation, xenodiagnoses, and hemoculture, show low sensitivities, limiting their usefulness. Microhematocrit is the method of choice to identify congenital infection because of its heightened sensitivity and the small amount of blood needed. Microscopic examination of cord blood or peripheral blood of the neonate by this technique is strongly recommended during the first month of life. For the monitoring of drug efficacy, the criterion of cure usually depends on serologic conversion of the anti-*T. cruzi* antibody response to negative. Sero-conversion in children and adolescents may occur several years after treatment, requiring long-term follow-up.

Sero-reduction (measured as a $\geq 20\%$ reduction of the ELISA absorbance [OD] value) at 12 months post-treatment will be considered equivalent to historical information on sero-conversion at subsequent time points after treatment.⁷²

Both primary and secondary study endpoints are based upon a target of $\geq 20\%$ decrease in antibody concentration (sero-reduction) to *T. cruzi* in conventional serological tests or negativization of serology. This is consistent with one previous study in children 6 to 12 years of age infected with *T. cruzi* in the intermediate (early chronic) phase of Chagas' disease [15]. Subjects were administered 5mg/kg benznidazole or placebo in a randomized fashion for 60 days, and followed for 48 months. At 12 months, a 21% reduction in concentration of Chagas' disease-specific antibodies compared to baseline (ELISA mean OD 0.467 [± 0.099] vs. 0.369 [± 0.107]) was observed in subjects who received benznidazole. For the subsequent time points of 18, 24, and 48 months, percent concentration reductions in antibody titer were reported as 23%, 29%, and 27%, respectively. After a 48-month follow-up, negative sero-conversion was detected in 11.3% (P<0.05) of the benznidazole group and only 4.5% of the placebo group.⁷³

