15.6.1 Overview of changes

The reason for Amendment 6 is to replace the immunofluorescent antibody (IFA) test introduced via Amendment 5 by the indirect hemagglutination assay (IHA).

Use of another serological test such as IFA or IHA was requested by FDA to validate the current ELISA test results. This test will be carried out at Visit 1 and Visit 11 using random back-up samples from the study subjects.

Rationale: Given that another type of assay has to be performed and the FDA recommended either IFA or IHA, the IHA is considered the more suitable assay compared to the IFA taking into account the number of samples to be analyzed and the time frame for performing the analyses.

Furthermore, the sponsor's responsible Global Clinical Leader has changed and the name was updated.

The associated changes to the protocol text are detailed in Section 15.6.2.

Sections affected include:

- List of abbreviations
- Signature of the sponsor's medically responsible person
- Synopsis, Diagnosis and main criteria for inclusion/exclusion
- Study objectives, Section 4
- Study design, Section 5
- Inclusion criteria, Section 6.1
- Tabular schedule of evaluations, Section 9.1
- Visit 1 screening visit (Days -14 to -1), Section 9.2.1.1
- Visit 11 (Day 420 ± 7), Section 9.2.3.3
- Serological tests (Section 9.4.2)
- Variables and planned statistical analyses, Section 10.3

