## 6.2 Efficacy

## 6.2.1 Part 1 (CHICO)

## 6.2.1.1 Primary efficacy variable and analysis

The primary efficacy variable will be sero-reduction (defined as  $a \ge 20\%$  reduction in optical density [OD]) or sero-conversion (defined as negative Immunoglobulin G [IgG] concentration) in the 60-day regimen group at 12 months post-treatment using two conventional ELISA serology tests. This sero-reduction (in subjects  $\ge 8$  months to < 18 years of age at randomization) or sero-conversion (in all subjects) is considered cure, and the primary variable is binary (cure, no cure). In the event of discordancy between the two conventional ELISA test results, the following will be considered:

• For sero-reduction, the average percentage of OD reductions for the two conventional ELISA tests will be used (e.g., Test #1 = 15% and Test #2 = 25%; average = 20% and, hence, cure).

BAY No. A2502/IMPACT No. 16027

Page:

- For sero-conversion, only when both test results are negative that the subject is considered as negative (i.e., cure).
- If one of the test results is missing, the subject is considered as "no cure".

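### The ELISA–IHA McNemar tests in SAP 6.2.1.3 use response categories that differ between the assays, so their p-values do not show whether the assays agree

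*SAP*

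**What the plan says.** SAP 6.2.1.3 compares conventional serology with IHA in three tables. Table 6-2 is a descriptive cross-tabulation. Tables 6-3 and 6-4 add McNemar's test by regimen, with a chi-square and a p-value.

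- **Table 6-3, whole FAS.** The ELISA split is "ELISA tests: cure (sero-conversion and sero-reduction) versus no cure". The IHA split is "IHA test: negative or positive but decreasing in titers versus positive but non-decreasing in titers".
- **Table 6-4.** "The same test would also be performed by treatment regimen in sero-positive subjects", with the ELISA split "ELISA tests: sero-reduction versus others (sero-positive that are not sero-reduction" and the same IHA split.

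SAP 6.2.1.1 defines the ELISA terms. Sero-reduction is an OD fall of at least 20%; when the two ELISAs disagree, "the average percentage of OD reductions for the two conventional ELISA tests will be used". Sero-conversion needs both ELISAs negative. Sero-reduction is tied to ages 8 months to under 18 years at randomization, "or sero-conversion (in all subjects) is considered cure, and the primary variable is binary (cure, no cure"). No section gives IHA a minimum fall or an age limit.

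The SAP lists the comparison as an exploratory objective (2.1). Protocol 15.6.1 gives the reason for the assay: "Use of another serological test such as IFA or IHA was requested by FDA to validate the current ELISA test results".

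**The concern.** McNemar's null hypothesis is that the two assays have equal response proportions. That stands for agreement between the assays only if response means the same thing on both. Here it differs in three ways.

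1. **Cut-off.** A still-positive child needs a 20% fall on ELISA but any recorded fall on IHA.
2. **Age (Table 6-3).** A child under 8 months who is still ELISA-positive cannot be a cure, however far OD falls. The same child is an IHA responder on any titer fall.
3. **Selection (Table 6-4).** Children negative on ELISA are removed; children negative on IHA stay in as responders.

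These p-values are the only inferential output for the comparison with IHA. For qPCR and non-conventional serology, SAP 6.2.1.2 instead uses matches and mismatches, phi and kappa. A small p-value could be taken for a conflict between the assays when it reflects the cut-offs. A large one could hide mismatches that offset each other.

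**Working it through.** The plan gives no power or expected discordance for these tests, so there is no stated figure to reproduce.

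**Inputs from the documents.** Two-sided alpha 0.05 (SAP 4.1). Arms of 200 and 100 (Protocol 10.4); the half-width of 0.12 stated there reproduces for these sizes: 1.96 × √(0.25/200 + 0.25/100) = 0.120. Two strata lie under 8 months with a target of 38 each, so 76 of 300: about 51 and 25 by arm at 2:1, leaving 149 and 75 older children. Mean OD 0.467 to 0.369 at 12 months on benznidazole (Protocol 5.1): 0.098/0.467 = 21% fall.

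**Step 1: same change on both assays, any fall registers on IHA.** Let b count children who respond on IHA only, and c those who respond on ELISA only. The uncorrected statistic is (b − c)²/(b + c). Every still-positive child with a fall above 0% and below 20% goes into b, as does every still-positive infant with a fall in Table 6-3. Nobody goes into c, so the statistic equals b.

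- b = 4: 4.00 exceeds 3.841, p = 0.0455.
- b = 6: continuity-corrected (6 − 1)²/6 = 4.17, p = 0.041; exact 2 × 0.5⁶ = 0.031.

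The chance of reaching 4 (uncorrected) or 6 (exact) is a binomial tail in n and the assumed share q in cell b:

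| n | q | uncorrected | exact |
|---|---|---|---|
| 200 | 5% | 99% | 94% |
| 100 | 5% | 74% | 38% |
| 100 | 10% | 99% | 94% |
| 51 infants only | 10% | 76% | 40% |

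**Step 2: simulation in children of 8 months and over.** The true log change is the same on both assays, with mean log(0.369/0.467). Assumed: SD 0.15–0.35 and assay noise SD 0–0.10. ELISA response is 51–53%.

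| IHA reading | IHA response | rejection, 149 children | rejection, 75 children |
|---|---|---|---|
| any fall registers | 74–94% | 99.9–100% | 99.9–100% |
| two-fold steps (assumed) | 34–40% | about 89–99% | about 58–84% |

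The direction reverses between the rows. On two-fold steps, adding 51 or 25 infants, 20% of them still ELISA-positive with IHA falling (assumed), lowers rejection to 13–63% because the mismatches partly cancel.

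**Step 3: are the categories the cause?** In a second model (percentage falls Normal, mean 10–40, SD 15 points, equal noise SD 10 points; all assumed), one 20% rule on both assays rejects in 4.4–6.1% of trials. The SAP categories reject in 98.7–100% of the same trials when any IHA fall registers. On two-fold steps, with the same fall read by both assays, they reject in 21–100%.

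**Step 4: the infant rule and the selection separately.** With exchangeable assays in older children, the infant rule alone rejects in 11–18%, 26–46% and 48–75% of 60-day trials if 10%, 20% or 30% of infants are still ELISA-positive with IHA falling. The Table 6-4 selection alone gives 4–25% across conversion of 5–25%, returning to about 5% if both assays must be positive.

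**Step 5: which replacement is matched?** With exchangeable assays (assumed: infants 70–90% negative, older children 3–10%, latent correlation 0.5–0.9), requiring both ELISAs negative against one IHA rejects in 23–91% (60-day) and 11–61% (30-day). Recombinant ELISA alone against IHA rejects in about 4–6%.

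**The case against.** The analysis is exploratory, with no decision rule and no link to the primary conclusion. Table 6-2 already prints every cell, so a reader can see where the discordance arises. That stands, and it limits how much rides on this point.

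Two readings go too far.

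- **That the tests will almost always reject, with IHA showing more response.** This needs IHA to register any fall, however small. IHA is scored in titers; if these move in steps, the smallest recordable fall is itself a threshold and IHA may be the stricter assay. The documents do not give the dilution scheme. Samples may also be smaller than simulated: Protocol Table 9-1 limits IHA to Visits 1 and 11 and to cases with enough specimen, and the stratum targets are not required.
- **That the age rule applies to both tables.** It is explicit only for cure, hence for Table 6-3. Table 6-4 uses sero-reduction, and the age limit reaches it only if the wording of the objective is carried over. The share of infants still positive is also unsourced. Protocol 5.1 reports negative conventional serology at 6.6 months (3.4–9.8) after benznidazole in those diagnosed under 8 months, which suggests the share could be small.

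The Table 6-4 selection adds little unless conversion is common. Protocol 5.1 reports 11.3% at 48 months on benznidazole at ages 6 to 12.

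None of this aligns the categories. Whichever way the direction falls, the p-value mixes the cut-offs with the behavior of the assays.

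**Conclusion.** The point holds. Tables 6-3 and 6-4 test equality of proportions that are defined differently, so a small p-value can arise when both assays record the same antibody change. As few as four to six one-sided discordant children per arm suffice, depending on the version of the test, which the SAP does not name. The mismatch is in the text; the rejection rates depend on the assumed spread, noise, infant share and IHA scale, and neither size nor direction can be fixed from the documents.

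A reader might infer that a small p-value would show IHA contradicting the ELISA cure endpoint, or that the Part 1 superiority conclusion is weakened. The documents support neither: the p-value does not separate cut-off from disagreement, and the primary analysis does not use IHA. The change should still be made, because these p-values do not address the stated objective of relating the two assays.

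**What to change.** In SAP 6.2.1.3:

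1. Remove the chi-square and p-value columns from Tables 6-3 and 6-4 as now categorised.
2. Keep the sero-reduction and titer-decrease cells descriptive, as in Table 6-2, and show them separately for under 8 months and for 8 months or older.
3. If an inferential comparison is wanted, use one assay against one assay: recombinant ELISA negative or positive against IHA negative or positive at Visit 11, by regimen. Report matches, mismatches and kappa, as SAP 6.2.1.2 does for qPCR. This is the pair that Part 2 uses (SAP 6.2.2.1).
4. Do not set both ELISAs negative against a single IHA. A two-test rule against one test is unmatched again, and it is not the Part 2 rule.

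If the tables have already been produced, report the p-values with a note on what they test.

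The cost is SAP wording and table shells; no new data are needed. The downside is that negativity at 12 months will come mainly from the youngest children, so the matched comparison will say little about older ones, and sero-reduction is left with a descriptive comparison only.
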